### 7.5.3 Stopping Rules (Criteria for Pausing of Study)

- 7.5.3.1 If at any time during the study one third (1/3) or more subjects experience an ERER assessed as possibly, probably or definitely related to study treatment, further enrollment and study treatments will be halted immediately until a thorough investigation has been conducted by the Medical Monitor and Principal Investigator.
- 7.5.3.2 After any SAE, potentially life threatening AE or death assessed as possibly, probably or definitely related to study treatment, further enrollment and study treatments will be halted immediately until a thorough investigation has been conducted by the Medical Monitor, Principal Investigator and IRB (if applicable).
- 7.5.3.3 If three or more subjects in this study, experience the same grade 3 or 4 adverse event, assessed as possibly, probably or definitely related to study treatment, further enrollment and study treatments will be halted immediately until a thorough investigation has been conducted by the Medical Monitor and Principal Investigator.
- 7.5.3.4 In the event of any unexpected Grade 4 toxicities, assessed as possibly, probably or definitely related to study treatment, further enrollment and study treatments will be halted immediately until a thorough investigation has been conducted by the Medical Monitor, Principal Investigator and IRB (if applicable).

- 7.5.3.5 The study will be halted for any report of Grade 3 anaphylaxis from immunotherapy/EP with INO-3112 in two or more patients (as graded per “Common Terminology Criteria for Adverse Events (CTCAE)”, version 4.03 issued by the US Department of Health and Human Services on June 14, 2010 (Appendix 4)).

## **8 STATISTICAL CONSIDERATIONS**

### **8.1 Sample Size Considerations**

Per Rose et al., the percentage of patients with grade 3 or 4 hematologic toxicity was 23%. With n=10 patients in this study, there is approximately a 92% chance of observing of at least one grade 3 or 4 hematologic toxicity. If 0 out of 10 adverse events are observed, the study provides 95% confidence that the true proportion of such events is <31%.

### **8.2 Safety Analysis**

With the toxicity results, data from the Acute Radiation Morbidity Scoring Criteria and CTCAE will be recorded for each patient during each visit. For the toxicity results, and for AEs and injection site reactions, descriptive statistics will be generated tabulating the percentage of subjects with events by type and grade along with associated exact 95% Clopper-Pearson confidence intervals.

### **8.3 Analysis of Immune Responses**

Binary responses, i.e., responders/non-responders, will be analyzed by calculating the percentage of responders along with associated exact 95% Clopper-Pearson confidence intervals. Continuous responses, e.g., immune levels, will be analyzed by calculating the mean or median responses along with associated 95% confidence intervals.

### **8.4 Analysis of Clinical Responses**

Disease status frequencies based on RECIST criteria categories will be summarized.

### **8.5 Summary of Demographic and Other Baseline Characteristics**

Demographic and baseline characteristics will be summarized with means, medians, standard deviations, ranges or percentages.

### **8.6 Missing Values**

Missing data will not be imputed.

### **8.7 Site Effects**

The data will be summarized by site and compared observationally among sites.

---

## **9 DATA COLLECTION, MONITORING, AND AE REPORTING**

### **9.1 Records to Be Kept**

CRFs will be provided for each subject. Subjects must not be identified by name on any CRFs. Subjects will be identified by their subject identification number (SID) provided by Inovio Pharmaceuticals, Inc.

### **9.2 Safety and Quality Monitoring and Record Availability**

#### Monitoring

Monitoring of the clinical trial will be performed by experienced monitors, who will report to the Sponsor. Records for all clinical subjects in this trial will be monitored. The following clinical site monitoring tasks will be performed at all sites:

- Prior to trial initiation, a site visit will be conducted to review all relevant forms and documentation, to ensure compliance with all applicable requirements.
- All clinical site monitoring visits will be documented.
- Periodic site visits will be performed on a per dose group basis.
- The site monitor will be responsible for addressing and documenting the following study conduct activities and obligations and will:
  - Assure that the study is being conducted in accordance with the protocol, applicable regulatory agency regulations, and IRB policies.
  - Discuss study conduct issues and incidents of noncompliance with the Investigator and/or study personnel and document them on the resolution trip report. Report any significant unresolved problems immediately to the sponsor.
  - Remind the Investigator as necessary of the obligation to immediately report SAE and provide subsequent follow-up report of the final outcome to the IRB.
  - Review all CRF pages for completeness, logic, and internal consistency throughout the study.
  - Assure that the study facilities continue to be acceptable.
  - Compare the study CRFs with source documents to assure that the data are accurate and complete and that the protocol is being followed.
  - Assure that investigational product and device accountability and reconciliation records are complete and accurate.
  - Assure that all subject specimens are being stored and forwarded properly for testing.

#### Record Availability

The investigator will make study documents (e.g., ICFs, drug distribution forms, CRFs) and pertinent hospital or clinic records readily available for inspection by the local IRB, the site monitors, the FDA, Inovio or its designee or confirmation of the study data.

### **9.3 Adverse Experience (AE) Reporting**

To assure the safety of the participants, information about all AEs (see Section 7.1 Safety Parameters for definitions), whether volunteered by the subject, discovered by investigator or study staff questioning, or detected through physical examination, laboratory test or other means, will be collected and recorded in the subject's source documents and followed as appropriate.

#### **9.3.1 Study Reporting Period of Adverse Events**

The reporting period for AEs due to chemoradiation therapy toxicity is the period immediately following initiation of chemoradiation through the Week 4 visit of the study.

The reporting period for all other AEs is the period immediately following informed consent through the end of the study

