**Table 1: HPV-004 Schedule of Events**

Tests	S	D0	Weeks a										
			2	4	6	8	10	12	14	16	24	32	36
Study Procedures													
Informed consent	X												
Medical and CIN/Cancer history	X												
Inclusion/Exclusion criteria	X	X											
Physical exam/assessment c	X	X	X	X	X	X	X	X	X	X	X	X	X
ECOG performance status	X	X	X	X	X	X	X	X	X	X	X	X	X
Medical/Clinical assessment	X	X	X b	X	X b	X	X b	X	X b	X	X	X	X
Chemo/RT Effects/Adverse Events	X m	X	X b	X									
Adverse events	X	X	X b	X	X b	X	X b	X	X b	X	X	X	X
Concomitant medications	X	X	X	X	X	X	X	X	X	X	X	X	X
Disease Status d	X									X		X	X
Vital signs (Height and Weight) e	X	X	X	X	X	X	X	X	X	X	X	X	X
12-lead ECG	X												
Histologic HPV assessment f	X												
Tumor biopsy collection	X l									X			
ThinPrep TM sample (if obtainable)	X	X								X			X
Digene swab (2) (if obtainable)	X	X								X			X
PET/CT scan	X n									X p		X q	X q
Laboratory Procedures													
CBC w/ differential	X	X o		X o		X o		X o		X o			
Serum chemistry g	X	X o		X o		X o		X o		X o			
Urinalysis h	X												
CPK	X									X o			
Pregnancy Test i	X	X		X		X		X		X			
HIV/ hepatitis serology	X												
Blood immunologic samples j	X	X				X				X	X	X	X
Immunotherapy Procedures													
Immunotherapy/EP		X		X		X		X					
Post treatment reaction k		X	X b	X	X b	X	X b	X	X b	X			
Download EP data		X		X		X		X					
Participant Reminder Card		X		X		X		X					
Review participant reminder card			X b	X	X b	X	X b	X	X b	X			

Wks 2, 6, 8 and 14 visits may be performed as an in-person office visit or a telephone call. After completing medical/clinical assessment, reviewing PRC and collecting information on AE with the subject on the phone, the investigator will determine whether an office visit is needed for further evaluation.

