Cohort 1: Subjects in Cohort 1 can be screened either prior to initiation of chemoradiation, or during chemoradiation and should be enrolled such that their first study treatment (Day 0) will be delivered within 2 weeks of completing their chemoradiation therapy;

Cohort 2: Subjects in Cohort 2 can be screened and enrolled such that their first study treatment (Day 0) is no sooner than 2 weeks and no later than 4 weeks after completing the salvage therapy. If in the

- 
- investigators opinion, there are no additional salvage therapy options, the subject may be enrolled in Cohort 2 without having received salvage therapy immediately prior to enrollment.
- a Procedures and visits scheduled from Day 0 through Wk 16 must occur  $\pm$ 1 week of scheduled time. Procedures and visits scheduled from Week 24 to Week 36 must occur  $\pm$  2 weeks of scheduled time.
- b assessment to be performed if visit done as phone-call
- c Targeted physical examination at all visits except full examination at screening (includes complete gynecological exam) and discharge visit
- d Disease status should be categorized into 1) No evidence of disease (NED) 2) Partial Response 3) Stable disease 4) Progressive disease
- e Temperature, respiratory rate, blood pressure, heart rate, weight and height. Height collected at screening only
- f Paraffin embedded tissue obtained for diagnosis of cervical cancer must be available for HPV testing
- g Serum chemistry includes glucose, albumin, total protein, SGPT, SGOT, alkaline phosphatase, total bilirubin, blood urea nitrogen (BUN), calcium, creatinine, electrolytes (sodium, potassium, chloride, carbon dioxide or bicarbonate)
- h Urine samples will be tested by dipstick for glucose, protein, and hematuria.
- i Serum pregnancy test required at screening. Urine pregnancy test should be used prior to tumor biopsy and prior to each study treatment/EP
- j At least 34 mL (4 x 8.5 mL tubes) whole blood in Acid Citrate Dextrose tubes and 4 mL serum per time point. A total of at least 68 mL whole blood and 4 mL serum should be collected prior to dosing on Day 0
- k Assessed 30 to 45 minutes after study treatment/EP and at post-treatment visits
- l A tumor biopsy collection is required at screening if residual tissue and/or unstained slides are not available

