- m Chemo/RT effects to be assessed at screening if subject is screened during chemoradiation
- n PET/CT to include standard uptake volume, must be performed within 4 weeks prior to Day 0
- o All labs for Day 0 and those associated with any treatment visit should be available prior to treatment and collected no more than 48 hours prior to treatment
- p PET/CT will be performed 3-4 months after Day 0
- q Not required at study discharge if performed at wk 32
- r Immune competence will be evaluated longitudinally throughout the study from the time of screening visit. No additional blood collection required.

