### 6.1.2 Study Evaluations

Visit dates and windows must be calculated from the date of the Day 0 visit.

The following study evaluations will be performed on **Day 0 prior to study treatment/EP 1:**

- Determination of eligibility per inclusion and exclusion criteria
- Medical/clinical assessment
- Targeted physical assessment (including ECOG performance status)
- AE/SAE event assessment
- Assessment of systemic reaction/toxicity/side effects of standard (chemoradiation) therapy to be completed immediately prior to the first study treatment/EP on Day 0
- Concomitant medications review
- Vital Signs and Weight
- ThinPrep™ sample for HPV testing (if applicable)
- Digene swab (2 samples) (if applicable)
- Complete blood count with differential
- Serum chemistry evaluation including glucose, albumin, total protein, SGPT, SGOT, alkaline phosphatase, total bilirubin, blood urea nitrogen (BUN), calcium, creatinine, electrolytes (chloride, carbon dioxide or bicarbonate, potassium, sodium)
- Urine pregnancy test
- Whole blood and serum for immunologic assays

---

The following study evaluations will be performed on **Day 0, post study treatment/EP 1:**

- Post-treatment adverse event and injection site reaction assessment within 30-45 minutes after EP
- Distribute Participant Reminder Card (PRC)
- Download EP data

The following study evaluations will be performed at **Weeks 2, 6, 10 and 14 post study treatment/EP (± 1 week):**

- Medical/clinical assessment \*
- Targeted physical assessment (including ECOG performance status)
- Assessment of systemic reaction/toxicity/side effects of standard (chemoradiation) therapy
- Post-treatment injection site reaction assessment\*
- AE/SAE assessment\*
- Concomitant medications review\*
- Review of PRC\*
- Vital Signs and Weight

Weeks 2, 6, 10 and 14 visits may be performed as an in-person office visit or a telephone call. The type of visit will be documented on the case report form. All study procedures listed above should be performed for an in-person visit. The assessments that are required for a telephone call are indicated above with an asterisk (\*).

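### RTOG-graded chemoradiation toxicity (primary safety endpoint 3) has contradictory visit schedules, and Section 8.2 does not separate toxicity before the first INO-3112 dose from toxicity after it

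*Combined protocol and SAP*

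**What the plan says.** The third primary safety endpoint in Section 3 is the rate of acute chemoradiation side effects above the expected, graded on the RTOG acute scale. These places govern when it is scored and how it is analysed:

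- **Table 1.** The row "Chemo/RT Effects/Adverse Events" is marked at Screening, Day 0, Week 2 and Week 4, with nothing later. The Screening mark is conditional: "Chemo/RT effects to be assessed at screening if subject is screened during chemoradiation". The Week 2 mark carries footnote b: "assessment to be performed if visit done as phone-call". The opening line of Section 6 sends the reader to Table 1 for procedure times.
- **Section 9.3.1.** "The reporting period for AEs due to chemoradiation therapy toxicity is the period immediately following initiation of chemoradiation through the Week 4 visit".
- **Section 6.1.2.** On Day 0 it requires the assessment of standard "therapy to be completed immediately prior to the first study treatment/EP on Day 0". Among the dosing visits it restricts the item to Week 4, in the pre-dose list. It also includes the item, unrestricted, in the list for "Weeks 2, 6, 10 and 14 post study treatment/EP". These visits may be by telephone, and "The assessments that are required for a telephone call are indicated above with an asterisk"; the RTOG item has no asterisk.
- **Section 8.2.** RTOG data are recorded at every visit, and the percentage of subjects with events is tabulated by type and grade with exact 95% intervals. No period is distinguished.
- **Appendix 5.** The criteria apply from the start of therapy through day 90.

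Sections 6.2.4.1 and 7.3 refer only to specified visits.

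**The concern.** The endpoint has no single definition in time. Under one set of passages, RTOG scoring describes the weeks after dose 1. Under another it reaches past dose 4, unless the visits are by telephone, in which case most of it is not required. A reader of the final table could not tell which doses the rate covers.

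The second issue is attribution. The primary objective is the safety of INO-3112 compared with what is expected from standard therapy. In Cohort 1 the chemoradiation-toxicity window opens weeks before the first INO-3112 dose. A table of subjects with any event in that window can therefore count toxicity that arose, and even ended, before the study product was given. Endpoint 1 is also classified by relationship to study medication; endpoint 3 is not.

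**Working it through.** **The plan's own figures.** Section 8.1 uses a 23% rate and n = 10. The chance of at least one event is 1 − 0.77^10 = 0.927, against the stated 92%. The two-sided upper 95% bound at 0/10 is 1 − 0.025^(1/10) = 0.308, against the stated <31%. Both reproduce and neither is in dispute. The rest is a comparison of passages.

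**Scorings after the first dose.** Doses are at Day 0 and Weeks 4, 8 and 12. Sections 6.1.2 and 7.3 place dosing-day assessments before the dose. Weeks 2 and 4 therefore follow dose 1, Week 6 follows dose 2, Week 10 follows dose 3 and Week 14 follows dose 4.

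| Source | Post-dose RTOG scorings | Doses followed by a scoring | Last scoring |
|---|---|---|---|
| Table 1, consistent with 9.3.1 | Weeks 2, 4 = 2 | 1 of 4 | Week 4 |
| 6.1.2, all visits in person | Weeks 2, 4, 6, 10, 14 = 5 | 4 of 4 | Week 14 |
| 6.1.2, all optional visits by telephone | Week 4 = 1 required | 1 of 4 | Week 4 |

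At Week 2 the telephone rules conflict directly: Table 1 footnote b has the assessment done by telephone, while 6.1.2 does not require it.

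**Appendix 5 window, Cohort 1.** Inputs: 25 fractions (Section 3), five per week (Appendix 3), and a visit window of ±1 week (Table 1 footnote a). Counting the first fraction as day 1:

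- Earliest last fraction: 4 × 7 + 5 = day 33. Taking Day 0 on that same day is the extreme case; later brachytherapy only moves it later.
- Week 6, early edge: 33 + 42 − 7 = day 68, so it can fall inside.
- Week 10, early edge: 33 + 70 − 7 = day 96, always outside.
- Week 14, early edge: 33 + 98 − 7 = day 124, always outside.

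For a course lasting the permitted 10 weeks, Day 0 is day 71 with no gap and day 85 with a 2-week gap. Week 4 then falls on day 99 to 113. Appendix 5 therefore also bears on the Table 1 schedule when the course is long. No such calculation is possible for Cohort 2, where salvage therapy may be chemotherapy alone or absent.

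**Pre-dose and post-dose.** In Cohort 1 the Section 9.3.1 window starts with chemoradiation, and Section 3 gives the first INO-3112 dose after chemoradiation is complete. Each subject has one pre-dose RTOG scoring (Day 0), or two if screened during chemoradiation. Section 7.1.1 counts conditions present before the study drug only if they worsen, and excludes conditions with onset before consent that are unrelated to a protocol procedure. Section 8.2 applies neither rule to RTOG scores and does not use the Day 0 score as a baseline.

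**The case against.** The strongest reply is that this is a drafting slip with an evident answer. Section 6 points to Table 1. Table 1, Section 9.3.1, the Week 4 restriction among the dosing visits and the 90-day limit all favour an early stop. The pooled list in 6.1.2 probably lacks a qualifier, and the every-visit wording in 8.2 may simply be loose. As the likeliest reading this stands. But the line in Section 6 is not a precedence clause, 6.1.2 is the list a site works from visit by visit, and the Week 2 telephone conflict remains. If the early stop is intended, endpoint 3 covers dose 1 only, and no passage says so.

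On the split, Section 7.1.1 does limit the problem for adverse events. A whole-window table is needed for comparison with standard therapy, and scores are kept by visit, so a later split would be possible. All of that stands. It supports keeping the whole-window table, but does not supply the missing one.

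Several stronger readings are tempting but unsupported:

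- **Toxicity after Week 4 is lost.** It is not. Sections 6.2.4.1 and 9.3.1 collect all other adverse events to the end of the study; what is not assured is RTOG grading.
- **Section 6.1.2 offers ready coverage of all four doses.** Appendix 5 stands in the way.
- **The Section 8.7 site comparison will be distorted.** Nothing shows that sites would follow different lists. Section 7.3 has an RTOG form completed for each patient, and Section 9.2 provides monitoring against the protocol.
- **An unsplit table would show an event with about 93% probability even if nothing followed INO-3112.** That would require the 23% in Section 8.1 to be a pre-dose rate. The documents do not say so, and inclusion criterion f requires hematology of Grade 1 or less at screening.
- **The telephone-week discrepancies change the endpoint.** The note "Wks 2, 6, 8 and 14 visits may be performed as an in-person office visit or a telephone call" includes Week 8, and Section 6.2.4.4 includes Week 12. Both are dosing visits for which 6.1.2 lists no RTOG item, so these are clerical errors.

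**Conclusion.** The point holds as a contradiction in the definition of a primary safety endpoint, together with a missing period split in its analysis. Its size is one of four doses against all four, a last scoring at Week 4 against Week 14, and two post-dose scorings against five, or one if the optional visits are by telephone. The 6.1.2 set cannot be adopted without addressing Appendix 5, because Weeks 10 and 14 always fall past day 90 in Cohort 1. That rests on the assumption of 25 fractions at five per week.

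No expected bias and no site effect is claimed. The documents do not give the number of subjects with toxicity only before dosing, or the cohort sizes. The matter should be fixed because the conflicting passages govern a primary endpoint and the correction is cheap. It does not put the capture of safety events in doubt.

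**What to change.** Reconcile Table 1, Sections 6.1.2, 8.2 and 9.3.1, and Appendix 5 to one set of RTOG visits and one requirement for telephone visits. State which INO-3112 doses endpoint 3 covers. If visits beyond day 90 are kept, say how the RTOG criteria apply there. If scoring ends at Week 4, say that the endpoint describes the period after dose 1.

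In Section 8.2, add a table of RTOG toxicity with onset or grade increase after the first INO-3112 dose, relative to the Day 0 pre-dose score, and base statements about INO-3112 on it. Keep the whole-window table, labelled as such, for comparison with published standard-therapy rates.

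Correct the stray telephone weeks (8 in the Table 1 note, 12 in Section 6.2.4.4) as a clerical matter.

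The cost is protocol and SAP wording plus one table. The Day 0 score is already required and every candidate visit is already scheduled. The limitation is that post-dose rates are not comparable with published whole-course rates, so the two tables must not be interchanged.

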#### **9.3.2 Study Reporting Period of Serious Adverse Events**

The reporting period for SAEs (without regard to causality) is the entire period following informed consent until the end of the study.

Each AE will be assessed to determine whether it meets seriousness criteria. If the AE is considered serious, the investigator should report this event to Inovio Pharmaceuticals as outlined below and also to the Ethics Committee according to its standard operating procedures.

Expectedness of SAEs will be determined by Inovio Pharmaceuticals using reference safety information specified in the Investigator's Brochure. An event may qualify for expedited reporting to regulatory authorities if it is a SAE, serious adverse drug reaction, or suspected unexpected serious adverse reaction (SUSAR) in line with relevant legislation. All investigators will receive a safety letter notifying them of relevant SUSAR reports. The investigator should notify the Ethics Committee as soon as is practical, of serious events in writing where this is required by local regulatory authorities, and in accordance with the local institutional policy. The investigator should send the initial report to sponsor within 24 hours of becoming aware of the event. At minimum, the initial report should include the following information:

- Event
- Study code
- Subject number, initials and date of birth
- Investigational study product
- Reporter name and contact information

In the case of a "minimum report" (one that is solely comprised of the information bulleted above), a more detailed follow-up report should be sent as soon as more information becomes available but no later than 7 calendar days after the date of the initial report. Each SAE should be followed up until resolution or stabilization and for a reported death, the

---

investigator should provide Inovio Pharmaceuticals and the Ethics Committee with any additional requested information (e.g., autopsy reports and terminal medical reports).

The original SAE form should be kept at the study site. Inovio Pharmaceuticals or its representative will be responsible for determining and in turn, reporting SAEs to regulatory authorities according to the applicable regulatory requirements.

SAEs must be followed by the investigator until resolution, even if this extends beyond the study-reporting period. Resolution of an SAE is defined as the return to baseline status or stabilization of the condition with the expectation that it will remain chronic.

At any time after completion of the SAE reporting period, if an investigator becomes aware of an SAE that is suspected by the investigator to be related to Study Treatment, the event should be reported to the Sponsor or its designee.

